4.1. Sample Size

Group sample sizes of 280 in each treatment arm will achieve at least 90% power to detect a difference in the percentage of participants with myopic progression (>0.75 D) of at least 15% between a SYD-101 arm and Vehicle. Power calculations presented in Figure 4-1 are based on the Chi-squared test at a 2-sided significance level of 0.025.

[figure not shown]
Figure 4-1 Power for 2-Sided Chi-Square Test Evaluated at Alpha=0.025 for Proportion Responders When 280 Participants Per Arm

Additionally, group sample sizes of 280 per treatment arm achieves >90% power to detect a reduction of 0.18 D or more in the annual progression rate between SYD-101 and Vehicle, assuming a common SD of 0.60 D. Power calculations presented in

Figure 4-2 are based on a 2-sample t-test evaluated at the 0.025 significance level.

Figure 4-2 Power for 2-Sided T-Test Evaluated at Alpha=0.025 for Annual Progression Rate When 280 Participants Per Arm

Furthermore, to estimate the statistical power of the two region- specific primary endpoints, simulations based on various assumptions regarding the mean vehicle annual progression rate, the mean active annual progression rate based on % reduction from the vehicle annual progression rate, the SD for the APR as well as allowing for participant dropout/study treatment discontinuation and escape medication have been considered to investigate statistical power for a range of sample sizes. Simulations were run after the protocol was finalized to assess protocol sample size assumptions. For the most likely assumption of parameters examined, a mean placebo/control APR of 0.65 D and a mean active APR 0.325 D (a 50% reduction from the mean vehicle/control APR) both with a SD of 0.55 D and an annual dropout/study treatment discontinuation rate of 7%, a sample size of 217 participants per treatment arm provides an approximate 97% power for the FDA endpoint and an approximate 99.96% power for the EMA endpoint assuming a significant level of 0.025.

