5.2. Protocol Deviations

Protocol deviations will be tracked by the clinical team on an ongoing basis based on the Protocol Deviations Rules document. The Protocol Deviation Rules document includes a description of identified potential deviations and assigns a rule number, deviation type (ICH/GCP Deviation vs. Protocol Deviation), deviation subtype (inclusion/exclusion criteria, visit scheduling, missing doses, treatment compliance, etc.), deviation type (efficacy vs. safety), significance (Significant vs. Non-Significant), deviation source (Medical Monitor Review, Site Monitoring, Automated Data Checks, etc.) and severity (Include Participant in All Analyses, Exclude Participant from PPS, Exclude efficacy assessments after date of deviation, Exclude efficacy assessment on the date of deviation, etc.) for each deviation. The Study Deviations Rules document may be updated as the study is ongoing and new deviations are identified. Each approved version of the Study Deviations Rules document will be maintained in the clinical project files.

Major protocol deviations are defined as the subset of deviations which are considered to have potential significant impact on analysis and results in the exclusion of a participant's data from analysis. Major protocol deviations that may be considered include, but are not limited to the following:

- Failure to fulfill any of the important inclusion/exclusion criteria
- Significant deviations in dosing adherence
- Taking prohibited medication or treatment listed in protocol Section 6.5.1
- Significant deviations in autorefraction process (e.g., only one autorefraction measurement taken per eye)

Participants with major protocol deviations will be tabulated by deviation sub-type for each treatment group. All percentages will be based on the number of FAS participants. Additionally, all major and minor deviations will be listed for all FAS participants.

6. Demographics and Baseline Characteristics

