8.1.1. Primary Analysis

Calculation of SE:

The primary efficacy endpoints for EMA and FDA are based SE. SE values will be calculated for each autorefraction for each eye as the sum of the sphere power with half of the cylinder power (SE = sphere + $\frac{1}{2}$ cylinder). The SE for each measurement will be calculated for each eye and then averaged by eye; the participant's averaged right eye SE and averaged left eye SE will then be averaged (i.e., a single averaged SE value for a given visit will be obtained for each participant by taking the “average of the averages”).

Per protocol, the autorefraction procedure is to be performed 3 times in each eye. If there are less than three measurements for a given eye, the available SE values will be averaged for that eye prior to averaging the right and left per eye SE averages for the final average SE (over both eyes) value for analysis. This final per participant average of SE from the right and left eyes will be used for analysis.

The final average SE (over both eyes) will be considered missing if a non-missing SE measurement is not available for both eyes at a given visit. For a given eye, SE is considered non-missing if there is at least one measurement with a non-missing sphere and a non-missing cylinder value recorded for the same autorefraction measurement. If the baseline final average SE (over both eyes) is missing from the autorefraction, the SE assessment result from the manual refraction will be used.

Data imputations:

A combination of hypothetical, composite, and treatment policy strategies for intercurrent events will be used for the primary estimands as detailed in Section 3.2. For the EMA and FDA, intermittent missing data or observations post study or treatment discontinuation not due to a related AE, will be multiply imputed using via Markov Chain Monte Carlo (MCMC) methods assuming the missing data is MAR (Missing at Random). However, for by eye analysis data will be analyzed as observed.

For the EMA, observations after specified prohibited or escape treatment will be observed until day of prohibited or escape treatment; observations following prohibited or escape treatment will be censored and not imputed. For the FDA primary estimand, observations post prohibited or escape treatment will be considered non-responders.

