For the EMA primary estimand, observations post study or treatment discontinuation due to a related AE will be multiply imputed assuming missing data is MNAR (Missing Not at Random). For the FDA primary estimand, observations post study or treatment discontinuation due to a related AE will be considered non-responders.

For the EMA and FDA, observations with invalid SE values will be analyzed as observed.

For any imputations, the value to be imputed is the average SE value (average of both eyes). This same set of imputed SE values will be used to calculate the primary efficacy endpoints for EMA and FDA, as well as the key secondary and applicable secondary efficacy endpoints derived from SE. All imputations will be based on set SEEDS. It is planned to perform k=50 imputations, however the number of imputations may be increased depending on the amount of missing data.

MAR imputations will be performed separately for each treatment arm and the imputation model will include terms for age at baseline, baseline SE (average of both eyes), and SE values (average of both eyes) for each post baseline scheduled visit through the specified analysis timepoint, Month 24 or Month 36 as applicable.

Imputations for data assumed to be MNAR will be first imputed via MCMC multichain methods to obtain monotone data as above for MAR imputations. The remaining missing SE values will be imputed via a sequential vehicle-based pattern imputation using regression methods ([Ratitch, 2011](#)) for the scheduled SE visits through the analysis timepoint, Month 24 or Month 36, using a model including age at baseline and baseline SE (average of both eyes) followed by sequential visits through M24 or M36, imputed values for those on SYD-101 treatment will be based on the Vehicle group.

Data sets will be sorted by treatment and participant id prior to imputation.

Valid SE Values:

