8.1.2. Sensitivity Analysis

Sensitivity analysis conducted for primary and key secondary endpoints using a combination of intercurrent event policies. Sensitivity Analysis 6 will be conducted for the confirmed progression > 0.75 D endpoint only, while Sensitivity Analysis 7 will be conducted for the annual progression rate primary endpoint only. Details for each sensitivity analyses are presented below and summarized in Appendix **Error! Reference source not found..**

1. [Sensitivity Analysis 1 \(PPS While on Treatment/Hypothetical\)](#)

For the EMA primary analysis repeated for PPS, intermittent missing data will be considered MAR and multiply imputed. Observations after prohibited medication/treatment or escape therapy will be censored and not imputed. Observations after treatment or study discontinuation due to a related AE will be multiply imputed assuming MNAR. All other observations after treatment or study discontinuation will be multiply imputed assuming MAR. Invalid SE values will be multiply imputed and assumed to be MAR.

For the FDA primary analysis repeated for PPS, intermittent missing data will be considered MAR and will be multiply imputed. Observations after prohibited medication/treatment or escape therapy will be considered non-responders. Observations after treatment or study discontinuation due to a related AE will be imputed as non-responders. All other observations after treatment or study discontinuation will be multiply imputed assuming MAR. Invalid SE values will be multiply imputed and assumed to be MAR.

2. [Sensitivity Analysis 2 \(FAS Treatment Policy for Prohibited Treatment, Escape Therapy and Treatment Discontinuation\)](#)

For the EMA the FAS intermittent missing observation will undergo multiple imputation assuming MAR. Observations after receipt of prohibited treatment, escape therapy or treatment discontinuation will be analyzed as observed. Observations after study discontinuation due to a related AE will be multiply imputed assuming MNAR with a vehicle-based imputation model. All other observations after study discontinuation will be multiply imputed assuming MAR. Invalid SE values will be analyzed as observed.

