For the FDA the FAS intermittent missing observation will undergo multiple imputation assuming MAR. Observations after receipt of prohibited treatment, escape therapy or treatment discontinuation will be analyzed as observed. Observations after study discontinuation due to a related AE will be imputed as non-responders. All other observations after study discontinuation will be multiply imputed assuming MAR. Invalid SE values will be analyzed as observed.

3. [Sensitivity Analysis 3 \(FAS MAR Tipping Point\)](#)

Data will first be multiply imputed for the FAS. Intermittent missing observations, observations after receipt of prohibited treatment or escape therapy, and observations after study discontinuation will undergo multiple imputation assuming MAR. For participants that discontinue treatment their observations will be analyzed as observed. Invalid SE values will be analyzed as observed. After imputations are performed, the tipping point method will be performed where a fixed value C is added to each SYD treatment imputed value. A range of values for C will be considered to identify the point at which statistical significance can no longer be claimed for either treatment arm.

4. [Sensitivity Analysis 4 \(FAS MNAR exclude Prohibited and Escape Observations\)](#)

For the FAS intermittent missing observations will undergo multiple imputation assuming MAR. All observations after receipt of prohibited treatment or escape therapy will undergo multiple imputation assuming not at random (MNAR) with a vehicle-based imputation model. For participants that discontinue treatment, their observations will be analyzed as observed. Observations after study discontinuation will undergo multiple imputation assuming MNAR with a vehicle-based imputation model. Invalid SE values will be analyzed as observed.

5. [Sensitivity Analysis 5 \(FAS MNAR include Vehicle post Prohibited and Escape Observations\)](#)

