For the FAS intermittent missing observation will undergo multiple imputation assuming MAR. SYD observations after receipt of prohibited treatment or escape therapy will undergo multiple imputation assuming MNAR with a vehicle-based imputation model. For the vehicle group, observations after receipt of prohibited treatment or escape therapy will have observed data included in the MNAR imputation model and used for analysis. For participants that discontinue treatment their observations will be analyzed as observed. Observations after study discontinuation will undergo multiple imputation

assuming MNAR with a vehicle-based imputation model. Invalid SE values will be analyzed as observed.

6. **Sensitivity Analysis 6** (confirmed progression endpoint only – all missing considered progression)

For the FAS and confirmed progression endpoint only, intermittent missing observations will be multiply assuming MAR. Observations after receipt of prohibited medication or escape therapy will be considered MAR and undergo multiple imputation. For participants that discontinue treatment, their observations will be analyzed as observed. If a participant discontinues the study prior to Month 24 or 36 (depending on analysis timepoint) and has not achieved a confirmed progression prior to their study discontinuation, then the participant will be considered a non-responder, regardless of reason for discontinuation. Observations of participants that discontinue treatment or have invalid SE values will be analyzed as observed.

7. **Sensitivity Analysis 7** (annual progression rate endpoint only - MMRM no imputations)

For the FAS and annual progression rate analysis only, multiple imputations will not be performed for missing data. Observations after receipt of prohibited medication or escape therapy will be censored (e.g., set to missing.) Observations of participants that discontinue treatment or have invalid SE values will be analyzed as observed. The MMRM approach treats missing data as MAR.

The same analyses as detailed in section 8.1.1 above will be repeated for each sensitivity approach above.

All imputations will utilize prespecified SET SEEDS that will be identified prior to unmasking at for the Month 24 analysis and documented in a programming appendix.

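### Sensitivity Analyses 3 and 6 change the FDA primary's failure rules along with its missing-data assumption, so neither isolates that assumption and the tipping-point value C cannot be read against the primary result

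*SAP*

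**What the plan says.** SAP 8.1.1 sets the FDA primary's rules: "For the FDA primary estimand, observations post prohibited or escape treatment will be considered non-responders", and "For the FDA primary estimand, observations post study or treatment discontinuation due to a related AE will be considered non-responders". Values missing after drug or study discontinuation for any other reason, and intermittent gaps, are imputed under MAR, separately by arm.

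SAP 8.1.2 then sets out seven sensitivity analyses.

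- **Analysis 3 (tipping point):** "observations after receipt of prohibited treatment or escape therapy, and observations after study discontinuation will undergo multiple imputation assuming MAR". Data after drug discontinuation are taken as observed. Neither rule has a related-AE exception. A constant C is then added to every imputed value in the SYD-101 arms.
- **Analysis 6 (titled as counting all missing data as progression):** "Observations after receipt of prohibited medication or escape therapy will be considered MAR and undergo multiple imputation". Intermittent gaps are also imputed under MAR, and data after drug discontinuation are taken as observed. A child who leaves the study without confirmed progression is failed, whatever the reason.

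SAP Appendix 14.1 and Protocol Table 9-3 describe both analyses in the same way.

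**The concern.** A tipping point is read as the departure from MAR needed to overturn the primary result. That reading requires the analysis to equal the primary when the departure is zero. Analysis 3 does not: it reclassifies children whom the primary counts as failures, and it replaces some values that the primary imputes with observed ones. A worst-case run should likewise be the primary plus extra failures. Analysis 6 adds failures for study dropouts but removes others, so some children whom the primary counts as progressed can become successes.

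If either analysis agrees with the primary, or disagrees, the reader cannot tell whether the missing-data assumption or the changed intercurrent-event rules produced the result.

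**Working it through.** **Rules side by side (FDA endpoint, full analysis set)**

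| Event | Primary | Analysis 3 | Analysis 6 |
|---|---|---|---|
| Prohibited treatment or escape | Fail | MAR, plus C on SYD-101 | MAR |
| Related-AE drug stop, followed up | Fail | Observed | Observed |
| Related-AE study exit | Fail | MAR, plus C on SYD-101 | Fail if not progressed |
| Drug stop, other reason | MAR | Observed | Observed |
| Study exit, other reason | MAR | MAR, plus C on SYD-101 | Fail if not progressed |

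Escape matters little here. Under SAP 3.5 it requires confirmed progression of at least 2.00 D, which already exceeds 0.75 D. Only escape outside the protocol criteria is affected.

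The other analyses do not fill the gap. Analysis 1 keeps the failure rules, but on the per-protocol set and with invalid SE values imputed. Analysis 2 uses observed data after prohibited treatment, escape and drug stopping. Analyses 4 and 5 use observed data after drug stopping and vehicle-based imputation after study discontinuation.

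**The plan's own figures first.** SAP 4.1 says "Group sample sizes of 280 in each treatment arm will achieve at least 90% power" for a difference "of at least 15% between a SYD-101 arm and Vehicle", at two-sided alpha 0.025. The normal-approximation power for 57.5% v 42.5% with 280 per arm is 0.907, which agrees. For the SAP simulation (0.65 v 0.325 D/year, SD 0.55, 7% annual dropout), take the 36-month change as normal with mean 3 × rate and SD 3 × 0.55 = 1.65:

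- Vehicle: p = Φ((1.95 − 0.75)/1.65) = 0.766
- SYD-101: p = Φ((0.975 − 0.75)/1.65) = 0.554
- Dropout by Month 36: d = 1 − 0.93³ = 0.196
- With 217 × 0.93³ = 174.5 completers per arm, power is 0.977, against a stated value of about 97%.

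**Expected difference under each rule set.** Let u be prohibited use and a be related-AE drug stopping with follow-up. Both are assumptions, taken as independent of progression, with imputed values progressing at the arm's own rate. Each arm's failure proportion is:

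- Primary: 1 − (1−u)(1−a)(1−p)
- Analysis 3 at C = 0: p
- Analysis 6: 1 − (1−d)(1−p)
- Analysis 6 with the primary's rules kept: 1 − (1−d)(1−u)(1−a)(1−p)

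*Case 1: u = 10% in both arms; a = 5% SYD-101, 1% Vehicle.*

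- Primary: 79.2 − 61.9 = 17.3 points
- Analysis 3 at C = 0: 76.6 − 55.4 = 21.2
- Analysis 6: 81.2 − 64.1 = 17.1
- Rules kept: 83.3 − 69.3 = 13.9 (unrounded inputs)

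*Case 2: u = 5% SYD-101, 15% Vehicle; a = 2% SYD-101, 1% Vehicle.*

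- Primary: 80.3 − 58.5 = 21.8 points
- Analysis 3 at C = 0: 21.2
- Analysis 6: 17.1
- Rules kept: 84.2 − 66.6 = 17.6

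**Could it change a conclusion?** Take base progression of 57.5% v 42.5%, 280 per arm, mutually exclusive events, a pooled z-test and threshold 0.025.

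*Case 3: prohibited use 5% per arm; related-AE drug stop 1% Vehicle, 5% SYD-101; related-AE study exit 0% and 3%; other dropout 12%.*

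- Primary: (1 − 0.94 × 0.425) − (1 − 0.87 × 0.575) = 10.1 points, p = 0.017
- Analysis 6: (1 − 0.88 × 0.425) − (1 − 0.85 × 0.575) = 11.5 points, p = 0.006
- Rules kept, all dropouts failed: (1 − 0.82 × 0.425) − (1 − 0.75 × 0.575) = 8.3 points, p = 0.045
- Analysis 3 tips when 48% of imputed SYD-101 non-progressors convert. With the rules kept, 10% of the non-progressors among the other SYD-101 dropouts suffice.

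*Case 4: prohibited use 10% Vehicle, 5% SYD-101; related-AE drug stop 2% and study exit 1%, SYD-101 only; other dropout 15%.* Analysis 3 tips at 46%, against 61% with the rules kept, so here Analysis 3 is the stricter check.

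**The case against.** The SAP says openly that its sensitivity analyses mix intercurrent-event policies, and Protocol 9.1.1 says the same, so the change of rules is deliberate. Both analyses also apply real pressure: C penalises imputed SYD-101 values after prohibited treatment and after related-AE study exit, and Analysis 6 fails every unprogressed study dropout. This stands, and it makes both analyses legitimate as supplementary work. It does not supply the missing analysis of the primary's own MAR assumption.

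A reader might infer that the changes favour SYD-101, or that the two analyses do not stress the primary at all. The documents support neither. They give no rates for prohibited use or related-AE stopping, SAP Table 3-2 itself expects that prohibited use may differ between arms, and Cases 2 and 4 go the other way. In Case 1, Analysis 6 is slightly below the primary.

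A reader might also extend the point to Analysis 1, because SAP 5.2 lists "Taking prohibited medication or treatment listed in protocol Section 6.5.1" among the deviations that can remove data. But Analysis 1 states the rule: "Observations after prohibited medication/treatment or escape therapy will be considered non-responders". SAP 5.2 only names deviations that might be treated as major, and it allows assessments after the deviation to be excluded while the child stays in. It is not established that the rule would fail to operate.

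The arithmetic is simple. The planned imputation conditions on each child's own SE history, and progression confirmed before the event still counts. The figures therefore illustrate size and direction and are not predictions.

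**Conclusion.** The point holds on the text. Analysis 3 drops the failure rule for prohibited treatment, off-protocol escape and both kinds of related-AE stopping, and it uses observed data where the primary imputes after drug discontinuation for other reasons. Analysis 6 drops the rule for prohibited treatment, off-protocol escape and related-AE drug stopping with follow-up, and its title is inaccurate. The tipping value C therefore has no reference point in the primary.

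In the illustrations, Analysis 3 starts between 0.6 points below the primary (Case 2) and 4.9 points above it (Case 3: 15.0 v 10.1). Analysis 6 lies between 0.5 points below and 3.2 points above its rule-preserving counterpart (Cases 1 to 4). These sizes rest entirely on assumed event rates.

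For the EMA primary, Analysis 3 replaces vehicle-based imputation with MAR only after related-AE study exit; after related-AE drug stopping it uses observed data. It would be wrong to say that MAR applies in both situations. The primary analysis itself and the power figures are unaffected.

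**What to change.** For the FDA endpoint, add two analyses on the full analysis set:

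1. **Tipping point.** Start from the primary's own imputed data sets and keep its composite failure rules. Shift only the SYD-101 values that the primary imputed under MAR, including those after drug discontinuation for other reasons. State that C moves SE in the more-myopic (negative) direction. At C = 0 this reproduces the primary exactly.
2. **All dropouts progressed.** Keep every primary failure rule, and also score any study discontinuation without confirmed progression as progressed.

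Keep Analyses 3 and 6 as supplementary, and retitle Analysis 6 to say that it fails study dropouts and not all missing data. Fix the wording before treatment codes are released. The cost is SAP text and two extra runs of existing code. The sponsor should accept that the stress tests may come out less favourable.
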